4.2.9.3 Vital signs and physical examination

For vital signs data, descriptive statistics for absolute value, change from baseline and percent change from baseline will be presented for each treatment group by scheduled visit and separately for the double-blind period and the OLE period. Summary statistics for continuous variables will include n, mean, standard deviation, median, minimum value and maximum value.

All vital sign and physical examination data will be listed.

4.2.9.4 ECG

The Investigator's overall evaluation of ECG (normal or abnormal) will be listed for all participants, detailing whether any abnormalities were clinically significant or not.

4.2.10 Tertiary/exploratory outcome variables

4.2.10.1 Peak Pruritus Numeric Rating Scale

The Peak Pruritus NRS will be summarized by descriptive statistics for observed means and mean changes from disease control of the weekly mean scores and the observed proportion of responders as per Section 3.6.1 by treatment group and week.

Peak Pruritus NRS assessment compliance will be also evaluated reporting descriptive summaries for each week.

4.2.10.2 Autoimmune Bullous Disease Quality of Life Questionnaire (AB-QoL)

The AB-QoL total score will be summarized presenting summary statistics for observed means and mean changes from baseline by treatment group and scheduled visit.

To support these summaries, an MMRM model may be fitted to this outcome variable if deemed appropriate, using the same statistical methodology detailed in Section 4.2.7.3 for the BPDAI activity score.

4.2.10.3 Serum and plasma biomarkers

Serum and plasma samples will be collected according to the CSP Table 2 to evaluate the pharmacology of benralizumab as well as biomarkers of eosinophil recruitment, activation, and survival (eg, absolute eosinophil count, IL-5, EDN, eotaxin). Summaries and plots of absolute levels and changes from baseline will be produced as appropriate.

To evaluate the association of baseline biomarkers with clinical efficacy, and assess for any markers potentially predictive of benralizumab treatment effect the following analysis techniques may be considered:

Scatterplots of baseline biomarker levels versus efficacy measures at Week 36, with locally weighted smoothing (LOESS) lines by treatment as appropriate

Subgroup analyses of proportion of participants in complete remission while off OCS for ≥ 2 months at Week 36 (and other efficacy endpoints if appropriate) by subgroups defined by baseline biomarker levels. Groupings of baseline biomarker levels may include splitting biomarkers at the median, or at quartiles if n large enough to warrant 4 groups, or other clinically relevant thresholds of interest to be pre-defined prior to unblinding. Results would be presented in forest plots of treatment effect in each level of the biomarker subgroups.

Additional markers of cellular inflammation and/or activation may be assessed including, but not limited to, those associated with humoral autoimmunity (total serum IgE, IgG directed against auto-antigens BP-180 and/or BP-230), T cell subsets (eg, IL-13, IFN-gamma, IL-17), eosinophil granule proteins (eg, MBP, eosinophil peroxidase), epithelial cell damage (eg, TSLP, IL-25, IL-33), itch (IL-31), and pain (substance P). The results from such studies will not be reported in the CSR but in separate reports or publications as appropriate. The corresponding analyses are not covered in this SAP.

CCI

CCI

4.2.11 OLE

The effect of benralizumab will be explored in participants in the OLE period by assessing endpoints as per Section 3.6.9.

These endpoints will be summarized using descriptive statistics for the OLE analysis set. Summaries will be presented for the overall population, and by prior randomized treatment (benralizumab or placebo).

In addition, selected efficacy and safety data may be integrated for those participants randomized to benralizumab, to describe efficacy and safety data over the entire study follow-up period, and on those participants who switch from placebo to benralizumab to describe efficacy and safety data over the benralizumab treatment period.

CCI

4.2.13 Relationship between IGA score and other measures of BP disease severity

The relationship between the IGA score and other measures of BP disease severity / activity will be explored via scatterplots and tabulations of endpoints. The types of outputs that may be produced include the following:

- Scatterplots of IGA score versus measures of disease activity such as physician global assessment and BPDAI score, at baseline, weeks 8, 16 and 36

- Cross tabulations of IGA score versus BP disease states at weeks 8, 16 and 36
- Cross tabulations of IGA score versus BPDAI severity (using BPDAI threshold of <24, ≥24 to <56 and ≥56 to as indicators of mild, moderate and severe disease) at baseline and weeks 8, 16 and 36
- Summaries of change from baseline in IGA score by PGI-C groups where PGI-C is categorised into groups of worsening, no change and improved

5 INTERIM ANALYSES

A non-binding futility analysis will be carried out by the IDMC when approximately [REDACTED] CCI randomized participants (ie, when approximately [REDACTED] CCI of the total amount of statistical information is available) have had the opportunity to complete at least 36 weeks of follow-up. Recruitment will remain ongoing while the futility analysis is performed. In the futility analysis, a predictive power-based guideline will be used for the primary endpoint (remission whilst off OCS for at least 2 months by Week 36) such that, given the data accumulated to date, if there is low chance ([REDACTED] CCI of achieving statistical significance at the final analysis if the study were to continue, then a stop decision for futility should be considered. [REDACTED]

[REDACTED] . If a decision is made that the study should continue, the primary analysis will be performed when all randomized participants have had the opportunity to complete at least 36 weeks of follow-up. The overall power is approximately [REDACTED] CCI after accounting for the inclusion of the futility analysis.

6 CHANGES OF ANALYSIS FROM PROTOCOL

Section 2.1.5 OLE analysis set has been added to identify all participants who enter into the OLE period.

In Section 3.1.5.2 further detail around which restricted medications are considered intercurrent events has been provided.

In Section 3.2 the missing data handling strategy for the primary endpoint has been detailed to cover occurrences of missing disease state assessments between two non-missing assessments. This is to integrate and not to change the approach specified in the CSP that states: “Any participant with missing data at a specific time point will be considered as a non-responder at that time point.” This statement in the CSP is meant to be applied to any missing disease state assessment after the last non-missing assessment.

In Section 4.2.7.3 the ANCOVA model specified for the analysis of the change from baseline at Week 36 in BPDAI activity score has been changed removing baseline disease severity as categorical covariate. This categorical variable is derived based on the baseline BPDAI activity score which is already included in the model as continuous covariate.

8 APPENDIX

8.1 Accounting for missing data

Missing data can occur due to intercurrent events, like usage of restricted medications and OCS dose increased, or early withdrawn. The amount of missing data is minimized in this study as participants are encouraged to remain in the study after premature discontinuation of IP and complete visits according to the protocol.

This section summarises how we will describe the pattern of and reasons for missing data from the study. It will also describe how we plan to account for missing data, including both the primary and sensitivity analyses to assess the robustness of the treatment effect under different underlying assumptions to account for missing data.

8.1.1 Missing data description

Tabular summaries for the percentage of participants by the reason for discontinuation of randomised treatment as well as for withdrawal from the study will be presented by treatment to describe why participants discontinue from randomised treatment or withdraw from the study. The time to discontinuation of randomised treatment and withdrawal from the study will be presented using Kaplan Meier plots (overall and split by treatment related/not treatment related reason for discontinuation, as defined in Table 9). Dependent on these outputs additional exploratory analyses may be produced as deemed necessary to further understand the pattern of missing data.

8.1.2 Primary analysis and key secondary main analyses

The primary analysis for the primary endpoint of proportion of participants who are in complete remission while off OCS for ≥ 2 months at Week 36 will be performed under a conservative assumption. Participants who experience any of the intercurrent events, including early withdrawn, are considered as non-responders. The analysis will include all the data up to Week 36, regardless of if they discontinue from randomised treatment.

The main analysis for the first key secondary endpoint of proportion of participants who remain relapse-free up to Week 36 will be analysed with a statistical model similar to the one described for the primary endpoint, under the same conservative assumption.

The analysis for the key secondary continuous endpoint of cumulative OCS exposure (mg/kg) from baseline to Week 36 and from baseline to Week 16 is performed imputing as missing data after the occurrence of intercurrent events, such as usage of restricted medications and OCS dose increased, or early withdrawal. The analysis uses the MMRM method and assumes that missing data is MAR and is a direct likelihood (DL) approach.

The analysis for the remaining key secondary endpoints, i.e. change from baseline in BPDAI activity score at Week 36 and change from baseline in BPDAI-Pruritus score at Week 36, will be performed with a composite strategy: participants who need to increase their OCS dose as a

rescue therapy to treat their BP after having previously achieved disease control will have their last BPDAI activity score observed carried forward. For participants who withdraw from the study without having rescue or restricted medications, missing BPDAI activity score at Week 36 will be imputed using multiple imputation based on participants who don't have rescue/restricted medication use. The same approach will be applied to those participants with missing data at Week 36 for any other reason.

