### **Cumulative OCS exposure (mg/kg) from baseline to Week 36 and from baseline to Week 16**

Two cumulative OCS exposure endpoints are defined: the cumulative OCS exposure over the 36-week double-blind period, and the cumulative OCS exposure over the first 16 weeks of the study. Each of these endpoints will be assessed from a mixed-effect model for repeated measures (MMRM), examining each participant's cumulative OCS exposure in 4-week periods. The cumulative exposure over the 36 (and 16) weeks will be estimated as the sum over the relevant 4-week periods from the MMRM model. This analysis method was selected to utilize all available data in the situation of any participants dropping out prior to 36 weeks. This ensures that any such participants can still contribute to the analysis for the period they remain in the study, without needing to make potentially implausible imputation assumptions around future OCS exposures in these situations (eg, carrying forward a high last observation of 0.75 mg/kg/d, which would not be a feasible dose to maintain for a 36-week period).

As highlighted in [Table 10](#), the intercurrent events of restricted medication use and study withdrawal will be handled with an effectiveness strategy, including all available data in the MMRM model until the occurrence of such events. As described above, this avoids needing to make potentially implausible imputation assumptions that a composite strategy would involve. Likewise, use of a treatment policy strategy is also not considered appropriate, as use of restricted medications would confound future OCS use. For example, if OCS were discontinued to receive another treatment due to lack of response or intolerance to OCS, the treatment policy approach would show a low cumulative OCS dose, which is a positive outcome and does not fairly represent the overall picture. Note that the list of intercurrent events does not include rescue with OCS (ie, increases in OCS dose after achieving disease

control), as by definition of the endpoint, increases in OCS dosing will be reflected in the cumulative OCS dose.

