3.1.5.2 Restricted medications

Restricted medications are detailed in the CSP Section 6.5.2 and will be selected considering a list of ATC codes that will be agreed and documented before unblinding (for the double-blind period) and final DBL (for the OLE period).

Only certain types of restricted medications used after randomisation during the double-blind period will be considered intercurrent events in the analyses, and only these cases will be handled as described in the estimand approaches detailed in Sections [4.2.6.1](#) and [4.2.6.2](#).

The restricted medications that will be considered intercurrent events include the following treatments if given to treat the participants BP, or if given for another condition but where prolonged use is deemed likely to substantially affect their BP outcomes:

- Immunosuppressive medications
- Anti-microbial agents with anti-inflammatory properties (eg. Tetracycline antibiotics, dapsone, erythromycin) – these are specific examples only, but review prior to unblinding will confirm if any others should be considered
- Topical corticosteroids
- Any marketed or investigational biologic (monoclonal or polyclonal antibody)
- Other IPs during the study or within 12 weeks after the last dose of benralizumab/placebo

In addition, for the endpoints where an increase in OCS use post disease control is considered an intercurrent event with consequence, this will only be in the case of OCS use with the aim of treating the participants BP, in a similar approach to the restricted medications described above. Short bursts of OCS use for other conditions (eg. COPD/asthma exacerbation) will not automatically trigger the estimand approach described.

A full review on concomitant medications will be performed prior to unblinding and the final list of intercurrent events will be confirmed and documented then.

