The set of intercurrent events for this estimand consists of participants who receive medications deemed to be intercurrent events as per Section [3.1.5.2](#) and participants who withdraw from the study. These events will be handled with an effectiveness strategy, including all available data in a Mixed-effect Model for Repeated Measures (MMRM) until the occurrence of such events. This avoids making potentially implausible imputation assumptions around future OCS use that a composite strategy would involve. For example, for a participant who discontinues at a high daily OCS dose early in the study, imputing a high daily OCS dose for the remainder of the treatment period would result in an imputed

cumulative OCS dose higher than participants would ever realistically receive. Likewise, using a treatment policy strategy is also not considered appropriate, as the use of restricted medications would confound future OCS use. For example, if OCS were discontinued to receive another treatment due to lack of response or intolerance to OCS, the treatment policy approach would show a low cumulative OCS dose, which is a positive outcome and does not fairly represent the overall picture.

Participants who receive medications deemed to be intercurrent events as per Section 3.1.5.2 will be considered with missing OCS exposure (mg/kg) from the date of start of restricted medications. Hence for the 4 weekly interval that includes this date, the OCS exposure will be computed by summing the recorded doses taken during only the days before the start of the restricted medications and rescaling them into a 4 weekly interval. For restricted medications during the study missing/partial start dates are not allowed.

Participants who withdraw from the study will be considered with missing OCS exposure (mg/kg) starting from the last contact with the participant. Hence the 4 weekly interval that includes this, the OCS exposure will be computed by summing the recorded doses taken during only the days before the last contact and rescaling them into a 4 weekly interval.

Note that the list of intercurrent events does not include increases in OCS dose after achieving disease control, and all doses of OCS will be included in the derivation of cumulative OCS exposure from baseline to Week 36/Week 16.

3.3.2.1 Cumulative actual OCS exposure (mg) from baseline to Week 36 and from baseline to Week 16

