	Treatment with benralizumab versus placebo, regardless of IP compliance	Cumulative OCS exposure (mg/kg) from baseline to Week 36 and from baseline to Week 16 (FAS)	
 • Treatment discontinuation – treatment policy • Restricted medication use – effectiveness (includes OCS dosing up to occurrence of event) • Study withdrawal – effectiveness (includes OCS dosing up to occurrence of event) 	Difference in mean cumulative OCS exposure (mg/kg) from baseline to Week 36 and from baseline to Week 16 (MMRM)	4.2.7.2

	Treatment with benralizumab versus placebo, regardless of IP compliance; rescue with OCS and restricted medication use indicate treatment failure	Change from baseline in BPDAI activity score at Week 36 (FAS), change from baseline in BPDAI-Pruritus score at Week 36 (FAS)	
 • Treatment discontinuation – treatment policy • Rescue with OCS^a – composite (LOCF) • Restricted medication use – composite (LOCF) • Study withdrawal – hypothetical (multiple imputation) 	Difference in mean change from baseline in BPDAI activity score/BPDAI-Pruritus score at Week 36 (ANCOVA)	4.2.7.3/ 4.2.7.4
Safety Objective: To compare the safety and tolerability of benralizumab with placebo in participants with symptomatic BP					
Safety	Treatment with benralizumab versus placebo, regardless of restricted medications.	
 • AEs • SAEs • Vital Signs • Physical examination (Safety) 	
 • Remained adherent to intervention (on-treatment) 	
 • Descriptive 	4.2.9

^a Rescue with OCS is defined as needing to increase OCS dose after previously having achieved disease control.

ANCOVA, analysis of covariance; BP, bullous pemphigoid; BPDAI, bullous pemphigoid disease area index; FAS, full analysis set; IP, investigational product; LOCF, last observation carried forwards; MMRM, mixed-effect model for repeated measures; OCS, oral corticosteroids.

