Results will be presented in terms of least square (LS) means of cumulative OCS exposure (mg/kg), treatment differences in LS means of cumulative OCS exposure (mg/kg), 95% CI and p-values for all scheduled visits. The cumulative OCS exposure (mg/kg) at Week 36 and Week 16 will be of primary interest. The LS means will be calculated using the OM option in the LSMEANS statement and the treatment-by-visit interaction to provide a LS means estimate for each scheduled visit. The LS means with 95% CIs will also be presented for each treatment group by scheduled visit.

P-values, corresponding to 2-sided tests, will be presented to compare the benralizumab and placebo treatment groups for each interval, including the whole of the 36-week treatment period and the initial 16-week treatment period.

The following SAS code is given as an example:

```
lsmestimate Treatment * 4WeeklyInterval  
  
'Treatment 1: 16 weeks' 0 0 0 0 0 0 0 0 0  
                      1 1 1 1 0 0 0 0 0,  
'Treatment 0: 16 weeks' 1 1 1 1 0 0 0 0 0  
                      0 0 0 0 0 0 0 0 0,  
'Diff: 16 weeks'    -1 -1 -1 -1 0 0 0 0 0  
                      1 1 1 1 0 0 0 0 0,  
'Treatment 1: 36 weeks' 0 0 0 0 0 0 0 0 0  
                      1 1 1 1 1 1 1 1 1,  
'Treatment 0: 36 weeks' 1 1 1 1 1 1 1 1 1  
                      0 0 0 0 0 0 0 0 0,  
'Diff: 36 weeks'    -1 -1 -1 -1 -1 -1 -1 -1 -1  
                      1 1 1 1 1 1 1 1 1  
/ om cl;
```

To support this analysis, observed means will be summarized using descriptive statistics by treatment group and 4 weekly interval, including the whole of the 36-week treatment period and the initial 16-week treatment period. Observed means will be also plotted by treatment group and 4 weekly interval.

To explore the uniformity of the detected overall treatment effect, the model might also be fitted considering OCS dose at randomization and its interaction with treatment as additional covariates.

The set of intercurrent events for this estimand and the imputation approach are detailed in Section 3.3.2. Since any BP relapses are expected to be treated with OCS (which is incorporated in the endpoint definition), the use of restricted medications which would result in exclusion of data beyond that point are expected to be infrequent. Therefore, the amount of missing data is expected to be low and is considered not likely to impact the results.

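### SAP Appendix 8.1.2 sets cumulative OCS exposure to missing after an OCS increase, against SAP 3.3.2, SAP 4.2.7.2 and Protocol 9.4.2.2; probably a drafting slip, but wrong as written for tests 3 and 6

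*SAP*

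**What the plan says.** SAP 8.1.2 is headed as covering the primary analysis and the key secondary main analyses. For cumulative OCS exposure to Week 36 and to Week 16 it describes an MMRM under missing at random, "imputing as missing data after the occurrence of intercurrent events, such as usage of restricted medications and OCS dose increased, or early withdrawal".

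The sections that define and analyse the endpoint read differently:

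- SAP 3.3.2 limits the intercurrent events to restricted medication and study withdrawal. It then adds: "Note that the list of intercurrent events does not include increases in OCS dose after achieving disease control". The same sentence goes on to say how steroid taken after such an increase is counted: "all doses of OCS will be included in the derivation of cumulative OCS exposure from baseline to Week 36/Week 16".
- SAP 4.2.7.2, the analysis section, states: "The set of intercurrent events for this estimand and the imputation approach are detailed in Section 3.3.2". Its reason for expecting little missing data begins: "Since any BP relapses are expected to be treated with OCS (which is incorporated in the endpoint definition").
- Protocol 9.4.2.2 says: "Note that the list of intercurrent events does not include rescue with OCS".
- SAP Table 8 and Protocol Table 10 handle restricted medication and withdrawal for this endpoint as "effectiveness (includes OCS dosing up to occurrence of event"). They have no line for rescue with OCS here, though both have one for the primary, relapse-free and BPDAI endpoints.

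SAP Section 6, which lists changes from the protocol, has no entry on this point.

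**The concern.** The endpoint exists to measure how much steroid a participant takes. If data are cut at the first increase after disease control, the steroid used to treat relapse is removed from it. Every participant's record would then end at rescue in both arms, so the MMRM would have no observed post-rescue exposure to learn from. It would predict later intervals from participants who had not been rescued. The quantity estimated would become exposure as if rescue had not been needed, and not exposure actually received.

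If benralizumab reduces rescue, this shrinks its apparent benefit. If benralizumab increases rescue, it hides harm.

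The endpoint is test 3 (Week 36) and test 6 (Week 16) in SAP 4.1.1, and the result at test 3 decides whether tests 4 to 6 are reached. Rescue may well be common: SAP 1.3 cites a trial with only 20% and 33% relapse-free to 36 weeks, and SAP 4.2.7.2 expects relapses to be treated with OCS. The primary and first key secondary endpoints are not affected.

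**Working it through.** **Comparison of the texts**

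| Place | Does an OCS increase end the exposure data? |
|---|---|
| SAP 8.1.2 | Yes, stated |
| SAP 3.3.2 | No, stated; all doses counted |
| Protocol 9.4.2.2 | No, stated |
| SAP 4.2.7.2 | No: points to 3.3.2 and treats relapse OCS as part of the endpoint |
| SAP Table 8, Protocol Table 10 | No, by omission |

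8.1.2 stands alone, and a program cannot follow both it and 3.3.2. A slip is the likely explanation. SAP 3.1.5.2 speaks of a rule "for the endpoints where an increase in OCS use post disease control is considered an intercurrent event with consequence", so it applies to some endpoints only. SAP 8.1.7 qualifies it by endpoint in the same way. The events listed in 8.1.2 are those of the BPDAI endpoints, where OCS rescue is an intercurrent event.

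**Size**

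The plan gives no figure for this endpoint. Its one power figure (85% for the primary endpoint, 50 per arm, 50% versus 20%) reproduces at 84.7% continuity-corrected or 85.3% by Fisher's exact test, and plays no part here. Two illustrations follow. The dose levels in them are arithmetic inputs only.

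*Illustration 1, one participant.* From the documents: the taper (20% per week to 10 mg, then 2.5 mg every other week; Protocol 6.5.1) and the rescaling of a cut 4-week interval (SAP 3.3.2). Assumed:

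- weight 80 kg and 40 mg/day (0.5 mg/kg) on Days 1–42;
- weekly steps of 32, 25.6, 20.48, 16.384, 13.107 and 10.486 mg on Days 43–84, then 10, 7.5, 5 and 2.5 mg for 14 days each;
- an increase on Day 92, after 7 days at 10 mg, with 14 days at the restart dose and then the same taper;
- missing values replaced by the unrescued course.

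Exposure from Day 85 under 8.1.2:

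- Days 85–112: (7 × 10 / 80) × 28/7 = 3.5 mg/kg.
- After Day 112: (14 × 5 + 14 × 2.5) / 80 = 1.3125 mg/kg.
- Total: 3.5 to Week 16 and 4.8125 to Week 36.

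Exposure from Day 85 with all doses counted, to Week 36:

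- Restart one step back: (70 + 14 × 10.486 + 350) / 80 = 7.085; lost 7.085 − 4.8125 = 2.27.
- Two steps back: (70 + 14 × 13.107 + 7 × 10.486 + 350) / 80 = 8.461; lost 3.65.
- Back to 0.5 mg/kg: (70 + 560 + 7 × 118.057 + 350) / 80 = 22.58; lost 17.77. Here 118.057 is the sum of the six weekly steps.

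To Week 16:

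- (70 + 146.80 + 70) / 80 = 3.585; lost 0.085.
- (70 + 183.50 + 73.40) / 80 = 4.086; lost 0.586.
- (70 + 560 + 224) / 80 = 10.675; lost 7.175.

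Shrinkage of the between-arm difference = loss × difference in rescue rates:

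| Restart | Week 36, 10 points | Week 36, 25 points | Week 16, 10 points | Week 16, 25 points |
|---|---|---|---|---|
| One step | 0.23 | 0.57 | 0.01 | 0.02 |
| Two steps | 0.36 | 0.91 | 0.06 | 0.15 |
| 0.5 mg/kg | 1.78 | 4.44 | 0.72 | 1.79 |

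All values are mg/kg.

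*Illustration 2, simulation.* This used 3000 per arm, nine 4-week intervals and an unstructured direct-likelihood fit. Assumed: disease control at 2–6 weeks, a starting dose of 0.5 mg/kg in 75% and 0.75 in 25%, uniform relapse timing, restart at 0.25–0.5 mg/kg/day and mean weight 72 kg. Benralizumab minus placebo at Week 36 (mg/kg):

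| Relapse, placebo / benralizumab | All doses (3.3.2) | Missing after increase (8.1.2) |
|---|---|---|
| 67% / 40% | −4.3 | −0.1 |
| 80% / 50% | −5.0 | −0.2 |
| 67% / 30% | −6.1 | +0.4 |
| 67% / 67% | +0.1 | +0.3 |

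Simulation error on the all-doses difference is about 13.4 × √(2/3000) = 0.35, taking the simulated placebo SD of 13.4. At Week 16 the differences stay below 0.5 in absolute value under both rules, because few simulated relapses come that early.

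**The case against.** The strongest reply is that the SAP already settles the conflict. SAP 4.2.7.2 sends both the derivation and the intercurrent events to 3.3.2, and it cites Appendix 8.1 only for multiple-imputation details in sensitivity analyses. SAP Section 1 says changes from the protocol will be described in Section 6, and none is described here. A programmer working in the normal order would follow 3.3.2. Harm needs someone to program from 8.1.2, and it also needs tests 1–2 (for test 3) or 1–5 (for test 6) to succeed. This stands, and it makes real damage unlikely.

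It does not remove the problem. SAP 8.1 says the appendix covers the primary analyses as well as the sensitivity analyses, and the heading of 8.1.2 names the key secondary main analyses. The SAP therefore states two rules for the same confirmatory tests.

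Smaller points also stand:

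- SAP 4.2.7.2 contradicts 8.1.2 partly by implication; only 3.3.2 and Protocol 9.4.2.2 do so in terms.
- The opening sentence of 8.1 is a general statement and is true for the BPDAI endpoints.
- The first illustration rests on a single profile. It uses the unrescued course as a stand-in for MMRM predictions and borrows a rescaling rule written only for restricted medication and withdrawal. Without that rule the 25-point figures become 0.68, 1.02 and 4.55 mg/kg at Week 36, and 0.13, 0.26 and 1.90 at Week 16.

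**Conclusion.** The contradiction is real, and 8.1.2 is the text that is wrong. It states for a confirmatory analysis a rule that the endpoint definition and the protocol both rule out. If 3.3.2 is programmed, tests 3 and 6 are unaffected. If 8.1.2 is programmed, the direction is clear: differences that arise through rescue shrink.

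The amount cannot be derived from the documents. The two illustrations range from negligible to nearly the whole Week 36 difference, and that spread comes from the assumed relapse timing, restart dose and rescue rates. The point should be fixed, as a correction of text and not a change of analysis.

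**What to change.** Edit the analysis text before unblinding:

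1. In the cumulative OCS sentence of SAP 8.1.2, delete the four words that name an OCS increase. Refer to 3.3.2 for the list of events, since the remaining wording would otherwise still read as open-ended.
2. In SAP 8.1.5, which imputes after the intercurrent event whatever its type, state that the events ending exposure data for this endpoint are restricted medication (per 3.1.5.2) and study withdrawal. Treatment discontinuation stays under treatment policy, as in Table 8.
3. Optionally, add to the opening sentence of SAP 8.1 the by-endpoint qualifier that 8.1.7 already uses.

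The cost is a few words, with no change to data collection, sample size or alpha. SAP 8.1.8 already plans an update on the sensitivity analyses before primary database lock. The 8.1.2 edit concerns a main analysis, but it can be made in the same update.
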